5.2.5 Patients randomized to the standard best supportive care arm

If a patient in the best supportive care arm requires hospitalization, the patient will be eligible to receive convalescent plasma if requested and/or deemed medically appropriate by the admitting physician. Administration of plasma will be performed as described in 5.2.2.

5.3 Withdrawal criteria

5.3.1 A subject must be withdrawn from study treatment for the following reasons

- Subject has experienced an unacceptable toxicity precluding the completion of plasma infusion.
- The study is terminated by the local health authority, or IRB.

5.3.2 If a subject is withdrawn from study treatment

- The reason(s) for withdrawal must be documented in the subject's medical record and in the CRF.
- The end of treatment (EOT) visit should be performed.
- Subjects must be followed for safety until the time of the follow-up visit or until study treatment-related toxicities resolve, return to baseline, or are deemed irreversible, whichever is longest.
- If the subject discontinues study treatment and actively withdraws consent for collection of follow-up data (safety follow-up or disease assessment), then no additional data collection should occur; however, subjects will have the option of withdrawing consent for study treatment but continuing in the follow-up period of the study.

5.4 Study Completion

5.4.1 A subject will be considered as completing the study if he or she meets any the following criteria:

- Subject completes the 2-month visit
- Subject dies, and a date of death is available
- Subject is known to have died; however, the date of death cannot be obtained (every effort must be made to obtain the date of death)
- Subject has discontinued study treatment and has withdrawn consent for collection of further follow-up data

6. Conduct of study assessment and procedures

6.1 Administration of informed consent form

Valid informed consent must be obtained from the study subjects, donor and patient, before conducting any study-specific procedures pertaining to donor or patient, using an ICF approved by the local IRB/IEC that contains all elements required by ICH E6 and describes the nature, scope, and possible consequences of the study in a form understandable to the study subject. Local and institutional guidelines for ICF content and administration must be followed; the original signed ICF must be retained by the investigator, and a copy of the signed ICF must be provided to the study subject. The informed consent process for each subject must be documented in writing within the subject source documentation. Rescreening of potential subjects is permitted. Recipient consent need not be obtained for a donor to consent and initiate treatment.

6.2 Prior and concomitant medications

The medication record will be maintained after signing the ICF to document concomitant medications.

6.3 Safety assessments

6.3.1 Adverse events

Adverse events for both donors and patients will be monitored from the time the subjects sign the ICF. Subjects will be instructed to report all AEs during the study and will be assessed for the occurrence of AEs throughout the study. In order to avoid bias in eliciting AEs, subjects will be asked general, nonleading questions such as "How are you feeling?" All AEs (serious and nonserious) must be recorded on the source documents and CRFs regardless of the assumption of a causal relationship with study treatment. The definition, reporting, and recording requirements for AEs are described in Section 8.

6.3.2 Performance status

Karnofsky performance status (table 1) will be assessed. Performance status must be assessed by a medically qualified individual and recorded in the CRF.

Table 1. Karnofsky Performance Status Grades:

Grade	Performance Status
100	Normal; no complaints; no evidence of disease.
90	Able to carry on normal activity, minor signs or symptoms of disease.
80	Normal activity with effort; some signs or symptoms of disease.
70	Cares for self; unable to carry on normal activity or to do active work.
60	Requires occasional assistance but can care for most of their personal needs.
50	Requires considerable assistance and frequent medical care.
40	Disabled; requires special care and assistance.
30	Severely disabled; hospital admission is indicated although death not imminent.
20	Very sick; hospital admission necessary; active supportive treatment necessary.
10	Moribund; fatal processes progressing rapidly.
0	Dead.

6.3.4 Infection monitoring

Monitoring for infection other than COVID-19 will be performed at +2 weeks (+/- 3 days), +4 weeks (+/- 3 days) and 2 months (+/- 5 days).

7. Safety Monitoring and Reporting

7.1 Adverse events

7.1.1 Definitions

For the purposes of this Protocol, an AE is defined as any untoward medical occurrence associated with the donation or use of a convalescent plasma for COVID-19 whether or not considered related, that occurs after a subject provides informed consent. Abnormal laboratory values or test results occurring after informed consent constitute AEs only if they induce clinical signs or symptoms, are considered clinically meaningful, or require therapy (eg, hematologic abnormality that requires transfusion).

7.1.2 Reporting

- Adverse events that begin or worsen after initiation of plasma donation or infusion should be recorded on the Adverse Events Form of the CRF. Monitoring for the occurrence of new AEs

should be continued for 1 days after the plasma donation and at least 60 days after the plasma infusion. Adverse events (including laboratory abnormalities that constitute AEs) should be described using a diagnosis whenever possible rather than by individual underlying signs and symptoms. When a clear diagnosis cannot be identified, each sign or symptom should be reported as a separate AE.

- If an adverse event meets the criteria for an SAE (eg, resulted in hospitalization, a life-threatening event, or death), the specific event(s) should be reported as an SAE(s).
- The severity of AEs will be assessed using CTCAE v4.03 Grades 1 through 5. If an event is not classified by CTCAE, the severity of the AE will be graded according to the scale below to estimate the grade of severity:

Grade 1 Mild; asymptomatic or mild symptoms; clinical or diagnostic observations only; intervention not indicated.

Grade 2 Moderate; minimal, local, or noninvasive intervention indicated; limiting age-appropriate activities of daily living.

Grade 3 Severe or medically significant but not immediately life-threatening; hospitalization or prolongation of hospitalization indicated; disabling; limiting self-care activities of daily living.

Grade 4 Life-threatening consequences, urgent intervention indicated.

Grade 5 Death due to AE

- The occurrence of AEs should be sought by nondirective questioning of the subject during the screening process after signing the ICF and at each visit during the study. Follow-up may occur remotely. This will apply for the donor where a post donation phone call will be placed. For the recipient, occurrence of AEs will be sought on days 0, +3 and +7 days by telephone (closest business day is acceptable), +2 weeks (+/- 3 days), +4 weeks (+/- 3 days). Adverse events may also be detected when they are volunteered by the subject during the screening process or between visits, or through physical examination, laboratory test, or other assessments. To the extent possible, each AE should be evaluated to determine:
 1. The severity grade (CTCAE Grade 1 to 5)
 2. Whether there is at least a reasonable possibility that the AE is related to the study treatment: suspected (yes) or not suspected (no)
 3. The start and end dates, unless unresolved at final follow-up
 4. The action taken about study treatment
 5. The event outcome (eg, not recovered/not resolved, recovered/resolved, recovering/resolving, recovered/resolved with sequelae, fatal, unknown)

- 6. The seriousness, as per SAE definition provided in section 7.2
- Unlike routine safety assessments, SAEs are monitored continuously and have special reporting requirements described in section 7.2.2.
- All AEs should be treated appropriately. If an AE is treated with a concomitant medication or nondrug therapy, this action should be recorded on the Adverse Event Form and the treatment should be specified on the Prior/Concomitant Medications or Procedures and Non-Drug Therapy Form in the CRF.
- Once an AE is detected, it should be followed until it has resolved or until it is judged to be permanent; assessment should be made at each visit (or more frequently if necessary) of any changes in severity, the suspected relationship to the study drug, the interventions required to treat the event, and the outcome.
- When the severity of an AE changes over time for a reporting period (eg, between visits), each change in severity will be reported as a separate AE until the event resolves.

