8.3.2 Safety Assessment

Safety assessment will be performed on infusion days 0 (post infusion), +3 and +7 days by telephone (closest business day is acceptable), +2 weeks (+/- 3 days), +4 weeks (+/- 3 days), 2 months (+/- 5 days). The safety of the trial will be accessed by evaluating the therapies exposure, adverse events (AE), and

death. Adverse events that begin or worsen after initiation of plasma donation or infusion should be recorded on the Adverse Events Form of the CRF.

A summarization of the number of days and/or cycles subjects were exposed to the therapies will be provided. AE (and serious adverse events, SAE) will be graded and recorded throughout the study and during the follow-up period according to the NCI Common Terminology for Adverse Events (CTCAE) v4.03. Toxicities will be characterized in terms regarding seriousness, causality, toxicity grading, and action taken with regard to trial treatment. The percentage of subjects experiencing an adverse event at a given severity, an NCI CTCAE toxicity grade, and the relationship to study therapy, will all be provided. And the number of subject deaths throughout the study will be summarized.

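### Adverse-event recording starts at consent in 6.3.1 but at donation or infusion in 7.1.2 and 8.3.2, so non-serious events may be captured unequally between the arms

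*Combined protocol and SAP*

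**What the plan says.** Two recording rules stand side by side in the combined protocol and SAP.

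- **Consent-anchored.** Section 6.3.1: "Adverse events for both donors and patients will be monitored from the time the subjects sign the ICF". It adds: "All AEs (serious and nonserious) must be recorded on the source documents and CRFs". Neither sentence depends on having received plasma.
- **Infusion-anchored.** Section 7.1.2 says of the form itself: "Adverse events that begin or worsen after initiation of plasma donation or infusion should be recorded on the Adverse Events Form of the CRF". Section 8.3.2, the safety analysis section, has the same rule: "Adverse events that begin or worsen after initiation of plasma donation or infusion should be recorded". Section 7.1.1 defines an AE as "any untoward medical occurrence associated with the donation or use of a convalescent plasma for COVID-19", although the same sentence also counts from informed consent.

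Section 6.3.1 does not say which rule governs. It defers: "The definition, reporting, and recording requirements for AEs are described in Section 8". The definition and reporting rules are in fact in Section 7, and Section 8 carries the infusion anchor.

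The schedule has the same split. Section 5.2 makes randomization day 0 for both arms, and 2.4 counts safety contacts for all patients from randomization. Section 8.3.2 counts them from infusion.

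For the end of observation, 7.1.2 requires monitoring for "at least 60 days after the plasma infusion". The recipient contact list in the same section ends at 4 weeks, as does the safety schedule in the Protocol Summary. Sections 2.4, 5.2.4 and 8.3.2 continue to 2 months.

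**The concern.** A Control patient has no infusion unless admitted to hospital, when 5.2.2 and 5.2.5 allow plasma. Under 7.1.2 and 8.3.2 that patient has either no start for form entry or a start that comes after the deterioration leading to admission. A Treatment patient has a start soon after randomization. COVID-19 itself will produce AEs in both arms, so a form filled in by the infusion-anchored rule would tend to hold more of the illness-related non-serious events from Treatment than from Control.

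Section 8 says that the trial assesses safety as well as efficacy against Control. Unequal capture would bias that comparison against plasma. The events missed in Treatment between randomization and infusion would bias it the other way, but over a much shorter period.

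**Working it through.** The documents give no figure to reproduce for the recording start. The check is a comparison of the text, followed by two short calculations.

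**1. Recording start under each rule**

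| Patient | Under 6.3.1 | Under 7.1.2 and 8.3.2 |
|---|---|---|
| Treatment, infused | Consent | Infusion, 0 to 48 h after randomization (5.2.2) |
| Control, never infused | Consent | None |
| Control, infused after admission | Consent | That infusion |

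A site could follow either column and point to protocol text in support.

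**2. What is collected whichever rule is followed**

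- Section 7.2.2 puts all serious adverse events (SAEs) on the form, with no infusion condition.
- Section 8.3.2 summarizes deaths throughout the study.
- Sections 5.2.3 and 5.2.4 schedule AE evaluation at day 3, day 7, 2 weeks, 4 weeks and 2 months without limiting it by arm.
- Section 7.1.2 itself has patients asked about AEs after consent and at every visit.

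What remains exposed is the entry of non-serious events on the form.

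**3. How many Control patients this concerns**

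Inputs: 153 Control patients if the trial reaches its final stage (8.2), and a planned Control hospitalization rate of 18% (8.1). Admission for worsening COVID-19 meets the SAE definition in 7.2.1.

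- Control patients with at least an SAE entry: 0.18 × 153 = 27.5, about 28.
- Control patients not admitted, and so with no infusion anchor: 153 − 28 = about 125.

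The non-serious events of these roughly 125 patients depend on which rule the site follows. So do those of the 28 before any infusion, or throughout if they receive none.

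**4. End of observation**

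Inputs: a 2-month visit with a window of ±5 days counted from randomization (2.4, 5.2.4), and infusion up to 48 h (2 days) after randomization (5.2.2). The length of 2 months in days is not stated; I assume 60 to 62.

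Earliest last visit, in days after infusion = length of 2 months − 5 − delay to infusion.

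- 60 days, delay 2: 60 − 5 − 2 = 53.
- 62 days, delay 2: 62 − 5 − 2 = 55.
- With infusion on day 0: 60 − 5 = 55 to 62 − 5 = 57.

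A visit at the early edge of the window therefore falls short of 60 days after infusion even with no delay. The 4-week end of the contact list in 7.1.2 falls short by about a month.

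**The case against.** The strongest reply is that the plan already collects AEs from everyone. Section 6.3.1 uses mandatory language for all AEs, while the sentence in 7.1.2 says only what should go on the form and does not expressly exclude other events. Visits, SAE reporting and the general statement in 8.3.2 that AEs are recorded throughout the study and follow-up apply to both arms. The safety endpoint in 2.4 concerns events associated with infusion, and 8.3.2 plans description, with no between-arm test. The CRF and the content of Appendix B cannot be seen, so actual practice cannot be judged.

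Much of this stands. A reader might infer that Control events have no recording start at all, that the Control column would be empty, or that the arms cannot be compared. The documents do not support that: 6.3.1 gives a start, and about 28 Control patients would have an SAE entry at the planned rate. A reader might also infer that the DSMB would mistake COVID-19 illness for plasma toxicity. That does not follow either, because 7.1.2 requires a relatedness assessment for each AE and 7.3 lets the DSMB ask for further data.

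The reply does not remove the contradiction. Section 6.3.1 hands the recording rules to a section that repeats the infusion anchor, so its own wording cannot be taken as decisive.

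On the 60-day rule, it is fair to say that other sections include the 2-month visit, that AEs volunteered between visits are accepted, and that SAEs are monitored continuously. The shortfall is in scheduled contact, not in all means of detection.

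**Conclusion.** The AE recording rules contradict each other on when recording starts and on how long observation lasts. If sites follow the infusion-anchored wording, non-serious events in uninfused Control patients (about 125 of 153 at the planned 18% admission rate and full enrollment) may be under-recorded, as may Treatment events in the up to 48 h before infusion. This is a risk of differential capture, and its size cannot be estimated from the documents because they give no expected rate of non-serious AEs. SAEs, deaths and scheduled AE questions are unaffected.

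The last scheduled visit can fall about 53 to 55 days after infusion, taking 2 months as 60 to 62 days and a 2-day delay to infusion, against the 60 days required. The plan should be corrected, because it sets out to assess safety against Control and 8.3.2 does not say that AE percentages will be shown by arm.

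**What to change.** - In 7.1.1, 7.1.2 and 8.3.2, remove the plasma-exposure condition for patients. Record all AEs in both arms on the same form from consent, as in 6.3.1, through the 2-month visit. Donor events can keep their own rule.
- In 8.3.2, state that AEs are tabulated by randomized arm, counting from randomization (day 0), with infusion-related events flagged as a subset. Starting the tables at day 0 while recording from consent gives both arms the same analysis period and leaves 6.3.1 intact.
- In 8.3.2, count the safety schedule from randomization, as 2.4 does.
- In 6.3.1, correct the cross-reference so that it points to Section 7.
- Reconcile the 60-day rule in 7.1.2 with its own contact list, the Protocol Summary and the window of the 2-month visit.

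The cost is an amendment of wording, a check that the CRF and Appendix B agree with it, and a note to site staff. Sections 5.2.3 and 5.2.4 already schedule AE evaluation for all patients, so unifying the recording start adds no visits.

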4.1 Overall study design

- This is a phase II randomized study of convalescent plasma for the treatment of non-immune individuals with COVID-19 infection at high risk of complications.

- Subjects will be considered as having completed the study after 2 months (+/- 5) days, unless consent withdrawal or death occurs first.
- Subjects will be randomized to receiving convalescent plasma or best supportive care.
- Patients randomized to best supportive care may receive plasma should they require hospitalization for progression of COVID-19 disease.
- Statistical analysis will be performed as described in the statistical section 8.
- The final analysis will be conducted once the last subject completes the 2-month visit or withdraws from the study.

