5.2 Patient procedures and evaluation (see Appendix B)

Patients may be screened, enrolled and randomized remotely. The day of randomization will be designated as day 0 for both Treatment and Control groups. Patients randomized to the treatment arm will need to be seen on the day of infusion which should occur within 48 hours of randomization and be within 96 hours of symptom onset.

5.2.1 Day 0. May be done remotely.

- Screening
- Informed consent must be obtained before performing study related activities (can be from healthcare proxy if subject unable to provide consent due to medical status)
- Baseline Evaluation (at screening)
 1. Demographics (age, sex ethnicity, race)
 2. Medical history
 - a. Date of onset of COVID-19 symptoms
 - b. Date of positive test
 - c. Acute and chronic medical conditions described in the eligibility criteria 3.2.
 - d. Charlson Co-morbidity Index calculation
 3. COVID-19 symptom screen (Y/N)
 - a. Fever (T Max)
 - b. Cough
 - c. Shortness of breath
 - d. Ageusia and/or anosmia
 - e. Myalgias
 - f. Headache
 - g. Other symptoms that the patient attributes to their COVID-19 infection
 4. Documentation of positive nasopharyngeal COVID-19 testing.
 5. Determination of eligibility as per inclusion/exclusion criteria
 6. Randomization

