5.2.2 Plasma infusion day

Patients randomized to the treatment arm will need to be seen on the day of infusion which should occur within 48 hours of randomization and be within 96 hours of symptom onset.

Study plasma administration will be allowed for the Control arm after hospital admission if requested by the patient's medical team.

- On the day of infusion, blood will be drawn for:
 1. Inflammatory markers

- a. D-Dimers
 - b. Ferritin
 - c. CRP
- 2. Serological testing: anti-SARS CoV-2 titers
- 3. Exploratory blood test for genomics (optional)
- 4. Exploratory blood test for cytokines/chemokines (optional)
- 5. Rectal swab for gut microbiome analyses, to be sent to the CDI if possible
- 6. CBC
- 7. Complete chemistry
- 8. ABO Rh

- Procedure:
 - 1. A single unit of approximately 400-500 mL of liquid fresh plasma or 2 units of fresh frozen plasma for a total of approximately 400 mL will be transfused at an approximate rate of 50 mL per hour x 30 minutes, then the rate may be increased up to 150 mL per hour until completion. If plasma availability does not allow for 2 units of FFP, a single unit may be administered.
 - 2. If possible, 10mL of plasma will be collected for research from the infusion line and sent to the CDI
 - 3. The infusion may be slowed or stopped as per investigator's decision for minor transfusion reactions only. The transfusion will be discontinued for any transfusion reactions other than minor allergic reactions.
 - 4. An investigation will be initiated when there are signs of a systemic transfusion reaction.
 - 5. Premedication 30 – 60 minutes prior to the infusion will include 100 mg hydrocortisone IV and may include acetaminophen 650 mg PO and diphenhydramine 25 mg IV. Diphenhydramine 25 mg IV and hydrocortisone 100 mg IV may be repeated as needed for an infusion reaction at the discretion of the investigator.
 - 6. Vitals signs should be monitored following Hackensack Meridian Health Blood and Blood Product Administration SOP guidelines:
 - a. Temperature, pulse, respirations, and blood pressure pre-infusion (within 30 minutes), 15 minutes after the start, every hour during, if a transfusion reaction is suspected or if there is any change in patient condition, post transfusion (5-15 minutes post)

5.2.3 Post enrollment day +3 and day +7 (or closest working day). May be done remotely.

- COVID-19 symptom screen by telephone (Y/N)
 - 1. Fever (T max)
 - 2. Cough
 - 3. Shortness of breath
 - 4. Ageusia and/or anosmia

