 - 5. Myalgias
 - 6. Headaches
 - 7. Other symptoms that the patient attributes to their COVID-19 infection

- New medical conditions, AE evaluation
- Safety assessment
- Rectal swab for microbiome at day +3 and day +7 to be sent to the CDI if possible.

5.2.4 Post enrollment: 2 weeks (+/- 3 days), 4 weeks and 2 months (+/- 5 days). Preferably in person.

- COVID-19 symptom screen (Y/N)
 1. Fever (T max)
 2. Cough
 3. Shortness of breath
 4. Ageusia and/or anosmia
 5. Myalgias
 6. Headaches
 7. Other symptoms that the patient attributes to their COVID-19 infection
- New medical conditions, AE evaluation
- Safety assessment
- Serological testing: anti-SARS CoV-2 titers if possible.
- Swab for COVID-19 testing at 2 weeks, and again at 4 weeks if week 2 is positive.
- Exploratory blood test for cytokines/chemokines at +2 and +4 weeks to be sent to the CDI if possible.
- Rectal swab for microbiome at +2 weeks, +4 weeks, and +2 months to be sent to the CDI if possible.

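### The 60-day adverse event window runs from infusion but study completion runs from randomization, so Control patients given plasma after about day 5 cannot be monitored for the stated period

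*Combined protocol and SAP*

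**What the plan says.** **The safety window.** Section 7.1.2 counts from the infusion: monitoring for new AEs "should be continued for 1 days after the plasma donation and at least 60 days after the plasma infusion".

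**The participation clock.** Section 5.2 states: "The day of randomization will be designated as day 0 for both Treatment and Control groups". The last scheduled visit, in 5.2.4, is "Post enrollment: 2 weeks (+/- 3 days), 4 weeks and 2 months (+/- 5 days). Preferably in person". Section 4.1 adds: "Subjects will be considered as having completed the study after 2 months (+/- 5) days, unless consent withdrawal or death occurs first". One of the completion criteria in 5.4.1 is "Subject completes the 2-month visit".

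**When plasma is given.** For the Treatment arm, infusion "should occur within 48 hours of randomization and be within 96 hours of symptom onset" (5.2.2). For the other arm, the same section says: "Study plasma administration will be allowed for the Control arm after hospital admission if requested by the patient's medical team". Sections 4.1 and 5.2.5 repeat that permission. None of the three gives a latest day. For these patients 5.2.5 refers back to 5.2.2 for how the plasma is administered and says nothing about follow-up afterwards.

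**The contact lists.** Section 7.1.2 says that, for recipients, "occurrence of AEs will be sought on days 0, +3 and +7 days by telephone (closest business day is acceptable), +2 weeks"; its list then ends at +4 weeks. The safety endpoints in the protocol summary also end at +4 weeks. Sections 2.4, 5.2.4 and 8.3.2 all include a 2-month assessment. Section 2.4 counts its contacts from randomization, whereas 8.3.2 labels day 0 as the infusion day.

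**The concern.** Two rules govern how long a plasma recipient is watched for new AEs, and they start from different dates. In the Treatment arm the dates are at most two days apart. In the Control arm they are separated by the time to admission and then to infusion, which the protocol leaves open. A site that follows the visit schedule exactly will then break the minimum in 7.1.2 for a Control patient infused late, without any deviation from the schedule itself.

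What is at stake is the end of the post-infusion window in patients who were ill enough to be admitted. The plan also does not say how AEs after crossover plasma will be tabulated. Section 8.3.2 reports percentages of subjects with AEs and makes no provision for a Control patient who has received the study product.

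**Working it through.** The plan gives no figure of its own for follow-up after infusion, so there is none to reproduce. The check is calendar arithmetic.

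**Inputs**
- Required monitoring: at least 60 days from infusion (7.1.2).
- Completion: 2 months +/- 5 days from randomization (4.1, 5.2, 5.2.4, 5.4.1). Assumption: 2 months = 60 days, so the window is day 55 to day 65. The range 59 to 62 days is shown below.
- Infusion day *d*: 0 to 2 for Treatment (5.2.2); open-ended for Control. Days 10 and 21 serve as examples because 8.3.1 and 8.1 use those two horizons for hospitalization.
- Scale: 18% Control admission rate (8.1) and 153 Control patients (8.2).

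**Formulas**
- Follow-up after infusion = (55 to 65) − *d*
- Shortfall = 60 − follow-up, if positive

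| Arm | Infusion day | Follow-up after infusion (days) | Shortfall, latest to earliest visit (days) |
|---|---|---|---|
| Treatment | 0 | 55–65 | 0–5 |
| Treatment | 2 | 53–63 | 0–7 |
| Control | 7 | 48–58 | 2–12 |
| Control | 10 | 45–55 | 5–15 |
| Control | 14 | 41–51 | 9–19 |
| Control | 21 | 34–44 | 16–26 |

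**Treatment at the nominal visit (day 60).** Follow-up is 60 − 0 = 60 to 60 − 2 = 58 days, a shortfall of 0 to 2.

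**Cut-off for Control.** At the latest permitted visit, 65 − *d* ≥ 60 requires *d* ≤ 5. With 2 months taken as 59 to 62 days, the latest visit is day 64 to 67 and the cut-off is day 4 to 7. Over the same range the worst Treatment shortfall (infusion on day 2, earliest visit) is 8 to 5 days.

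**Is infusion after day 5 plausible?** Section 1.4 reports that most patients admitted at the site were in their second week of illness. Enrolment requires onset within 96 hours. Taking the second week as days 8 to 14 of illness and subtracting 0 to 4 days puts admission at about study day 4 to 14, mostly past the cut-off. This is indicative only, because it describes a different group of patients and gives no infusion dates.

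**How many.** 0.18 × 153 = 27.5, or about 28 Control patients admitted at full enrolment. If the trial stopped at the first or second analysis, the figures would be 0.18 × 51 = 9.2 or 0.18 × 102 = 18.4. All three assume that every admitted Control patient is infused.

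**Does other text close the gap?** Section 7.1.2 follows an AE already detected until it resolves or is judged permanent, and says SAEs are monitored continuously. Section 5.3.2 extends safety follow-up for subjects withdrawn from study treatment. Neither schedules a contact for new AEs after completion in a Control patient infused late.

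**The case against.** The case for leaving this alone has several sound parts.

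- **Treatment arm.** The shortfall is visit tolerance set against a round 60 days, and 7.1.2 allows remote follow-up, so one call can satisfy both rules. This stands, and the Treatment arm is a minor part of the point.
- **Contact list.** A reader might infer from 7.1.2 that AE collection stops at 4 weeks, leaving Treatment patients only 23 to 31 days (day 25 to 31, less 0 to 2). The documents do not support that. Sections 2.4, 5.2.4 and 8.3.2 schedule a 2-month assessment, and 7.1.2 also has AEs sought at every study visit. The missing entry is a drafting omission.
- **Anchor.** A reader might infer that every contact is counted from randomization. Section 8.3.2 uses infusion as day 0. If that clock also covered crossover infusions, follow-up would be 55 to 65 days. But 8.3.2 does not say so, and its wording conflicts with 2.4 and 5.2, so it adds an inconsistency without resolving one.
- **AE-rate endpoint.** A reader might infer that crossover gives the 2.4 rates unequal exposure windows. Section 2.4 limits that endpoint to outpatient infusion, and Control patients are infused only after admission, so on its wording they fall outside it. The summary omits the limit, so the point needs a statement but cannot be asserted as a bias.
- **Extent of loss.** Crossover recipients are still seen up to the 2-month visit, detected events are followed, and section 1.3 calls late events rare. This limits the harm to the tail of the window but does not remove the contradiction.

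Appendix B, the recipient schedule, appears in the reviewed text only as a heading, so its contents could not be checked.

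**Conclusion.** The plan is wrong as written on this point. Its visit schedule cannot deliver the post-infusion monitoring that 7.1.2 requires for a Control patient infused after about day 5 (day 4 to 7, depending on how 2 months is counted). The shortfall is 5 to 15 days for infusion on day 10 and 16 to 26 days for infusion on day 21.

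The number affected is bounded at about 28 of 153 at the assumed 18% rate. That is a ceiling: plasma is given only on request or if judged appropriate, uptake is not stated, and infusions by day 5 can still comply if the last visit is late. It would therefore go too far to say that nearly every crossover recipient is affected. Nor does every subject reach the 2-month visit, since 4.1 excepts earlier death and withdrawal of consent.

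The conclusion rests on there being no follow-up provision for crossover infusions outside the text available here. The primary endpoint is not affected. No judgement is made on whether 60 days is the right length.

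**What to change.** 1. Reconcile 4.1, 5.2.5, 5.4.1, 7.1.2, 8.3.2 and the summary to one stated safety clock, including whether day 0 is randomization or infusion. Word it so that anyone given study plasma, in either arm, is followed for the post-infusion period that the protocol itself states. The remote contact already allowed in 7.1.2 is enough.
2. In 5.2.5, say what safety follow-up applies after a crossover infusion, not only how the plasma is given.
3. Add the 2-month assessment to the contact lists in 7.1.2 and the summary.
4. In 8.3.2, report AEs after crossover plasma separately, by infusion received, and state whether they belong to the outpatient endpoint in 2.4.

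The cost is protocol wording, a few extra calls per crossover recipient, and one call for a Treatment patient whose last visit comes early. Final safety data could arrive a few weeks later: a Control patient infused on day 21 reaches 60 days on day 81, which is 16 to 26 days after the present completion window of day 55 to 65.
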